8.1 Definitions

For consistency of labeling and categorizing adverse events, the Food and Drug Administration (FDA), Code of Federal Regulations (CFR) title 21, part 312 Investigational New Drug Application – safety report guidelines, April 1, 2013 will be used in this study.

<http://www.accessdata.fda.gov/scripts/cdrh/cfdocs/cfcfr/CFRSearch.cfm?fr=312.32>

National Cancer Institute (NCI) Common Terminology Criteria for Adverse Events, Version 4.0 will be used for grading of adverse events in this study. NCI CTC Version .0, DCTD, NCI, NIH, DHHS; June 14, 2010, publish date: May 28, 2009 (<http://ctep.cancer.gov>).

Adverse event: An adverse event (AE) is any untoward medical occurrence associated with the use of a drug in humans, whether or not considered drug related.

Life-threatening adverse event or life-threatening suspected adverse reaction: An adverse event or suspected adverse reaction is considered "life-threatening" if, in the view of either the investigator or sponsor, its occurrence places the patient or subject at immediate risk of death. It

does not include an adverse event or suspected adverse reaction that, had it occurred in a more severe form, might have caused death.

Serious adverse event or serious suspected adverse reaction: An adverse event or suspected adverse reaction is considered "serious" if, in the view of either the investigator or sponsor, it results in any of the following outcomes: Death, a life-threatening adverse event, inpatient hospitalization or prolongation of existing hospitalization, a persistent or significant incapacity or substantial disruption of the ability to conduct normal life functions, or a congenital anomaly/birth defect. Important medical events that may not result in death, be life-threatening, or require hospitalization may be considered serious when, based upon appropriate medical judgment, they may jeopardize the patient or subject and may require medical or surgical intervention to prevent one of the outcomes listed in this definition. Examples of such medical events include allergic bronchospasm requiring intensive treatment in an emergency room or at home, blood dyscrasias or convulsions that do not result in inpatient hospitalization, or the development of drug dependency or drug abuse.

Suspected adverse reaction: A suspected adverse reaction means any adverse event for which there is a reasonable possibility that the drug caused the adverse event. For the purposes of IND safety reporting, "reasonable possibility" means there is evidence to suggest a causal relationship between the drug and the adverse event. Suspected adverse reaction implies a lesser degree of certainty about causality than adverse reaction, which means any adverse event caused by a drug.

Unexpected adverse event or unexpected suspected adverse reaction: An adverse event or suspected adverse reaction is considered "unexpected" if it is not listed in the investigator brochure or is not listed at the specificity or severity that has been observed; or, if an investigator brochure is not required or available, is not consistent with the risk information described in the general investigational plan or elsewhere in the current application, as amended.

Lupus Flare

A lupus flare is any significant worsening of the signs, symptoms and laboratory test abnormalities associated with lupus. These changes are captured and graded in the BILAG 2004 and will be considered part of the safety information for this study. The details of the BILAG grading system are provided in appendix A. In general, the following approach is used:

- Mild lupus flare (Grade 1): New BILAG 2004 grade C in one or more organ systems.
- Moderate lupus flare (Grade 2): New BILAG 2004 grade B in one or more organ systems.
- Severe lupus flare (Grade 3): New BILAG 2004 grade A in one organ system.
- Life-threatening or disabling lupus flare (Grade 4): A life-threatening or disabling new BILAG 2004 grade A.

Signs, symptoms and laboratory test abnormalities reported as part of a lupus flare will not be separately reported as an adverse event using the *FDA-CFR Code of Federal Regulations Title 21, Part 312 Investigational New Drug Application definitions*.

8.2 Collection and Recording of Adverse Events

8.2.1 Collection Period

Adverse events will be collected from the time of initiation of study intervention (i.e., the first dose of study drug) until he/she completes study participation on Day 84 or until 30 days after he/she prematurely withdraws from the study. In the event of an adverse event, the first concern will be for the safety of the patients. Investigators are required to collect and document all adverse events (AEs).

8.2.2 Collection of Adverse Events

Adverse events (including SAEs) may be discovered through any of these methods:

- Observing the subject.
- Questioning the subject in an objective manner.
- Receiving an unsolicited complaint from the subject.

In addition, an abnormal value or result from a clinical or laboratory evaluation (including, but not limited to, a radiograph, an ultrasound, or an electrocardiogram) can also indicate an adverse event. If this is the case, then the evaluation that produced the value or result should be repeated until that value or result returns to baseline or can be explained and the subject's safety is not at risk. If an abnormal value or result is determined by the investigator to be clinically significant or NCI CTCAE Grade 1 and above, it must be recorded as an adverse event. Once recorded, an AE will be followed until it resolves with or without sequelae, or becomes medically stable.

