Exclusion Criteria

Subjects who meet any of the following criteria are disqualified from enrollment in the study:

1. Current or prior treatment with rituximab or anti-CD22 monoclonal antibody in the 12 months prior to this study or any other biologic agent for 90 days prior to this study
2. Treatment with cyclophosphamide within the 6 months prior to screening
3. Increase in glucocorticoid dose within 4 weeks of screening or addition of a DMARD in the three months prior to study
4. A history of drug or alcohol abuse within the 6 months prior to screening
5. Elevated LFT's:
 - ALT or AST ≥ 2 x upper limit of normal at screening
 - serum unconjugated bilirubin > 3 mg/dL at screening
6. Dialysis or serum creatinine >1.5 mg/dL
7. Hypercholesterolemia: total cholesterol >230 mg/dL or LDL >150 mg/dl or hypertriglyceridemia (triglyceride >200 mg/dL) at screening
8. Laboratory/clinical evidence of: pancreatitis: amylase/lipase >3 x upper limit of normal at screening
9. Known current/active infections including HIV, Hepatitis B, Hepatitis C
10. History of cancer, excluding skin cancers (squamous cell or basal cell that have been treated)
11. Known active tuberculosis or untreated tuberculosis
12. Hemoglobin < 8 g/dL
13. Expectation by the investigator to increase corticosteroid or immunosuppressive, or immunomodulatory medication dose at screening, baseline, or over the course of the study
14. Pregnancy or lactation
15. Consumption of > 2 cups of grapefruit juice per day
16. Treatment with medications metabolized using the cytochrome P3A4 pathway, such as cyclosporine, tacrolimus, gemfibrozil, niacin, itraconazole, ketoconazole, erythromycin, azithromycin, clarithromycin, bosentan, nefazodone, tricyclic antidepressants
17. Treatment with any drugs known to interact with nelfinavir that include amiodarone, quinidine, midazolam, triazolam, ergotamine, dihydroergotamine, methylergonovine, pimozide, lovastatin, simvastatin, rifampin, St. John's Wort, aluzosin, cisapride and sildenafil.
18. Any condition that, in the opinion of the Investigator, would jeopardize the subject's safety following exposure to the study drug.

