Serum samples for anti-dsDNA antibodies from individual subjects on Days 1, 14, 28 and 56 will then be run simultaneously in the Core Laboratory in the North Shore/LIJ Health System using an enzyme immunoassay. This will allow for an ongoing statistical analysis of response so that the rules of the Simon Two Stage design can be applied. Mechanistic blood samples collected on Day 84 can all be frozen as individual subjects complete the study and all of these samples can then be batched at the participating sites and sent to the Coordinating Center at the FIMR at study completion.

[figure not shown]
2. Secondary endpoints

a) Safety

Safety will be evaluated by determining the frequency of adverse events and serious adverse events including measurements of hematology, clinical chemistry, lipid profile and urinalysis parameters over the course of the study from baseline to day 56. Safety will also be determined by assessment of disease activity. All adverse events will be mapped into their MedDRA preferred terms and assessed according to criteria established by the National Cancer Institute—Common Terminology Criteria version 4 [NCI-CTCAE].

The Simon Two-Stage trial is an open-label trial with no placebo arm. We felt justified in including no placebo arm for the following primary reasons: (i) nelfinavir is safe and well-tolerated in HIV patients, (ii) after excluding subjects taking contraindicated medications, we have no reason to think that those enrolled will be at increased risk for toxicity to nelfinavir, (iii) we are dosing at or below the recommended dose of nelfinavir in HIV patients, (iv) we have carefully pre-determined stopping rules for toxicity, and (v) as an added immediate safety precaution, we will enroll the first four subjects sequentially with a 2 wk observation delay prior to enrolling the next subject.

To identify immediate unexpected toxicity issues, the first 4 subjects will be enrolled sequentially and each will be observed for 2 weeks prior to enrolling the next subject (Fig. 6). In

all subjects, safety will be evaluated by the frequency of Adverse Events (AEs), serious AEs and changes in disease

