6. STUDY WITHDRAWAL OR DISCONTINUATION

6.1 Discontinuation of Protocol-Specified Treatment Requirements

A subject is considered to have completed the study when he/she has completed the Day 84 visit. Protocol-specified requirements for the treatment of subjects will be discontinued for subjects under the following conditions:

1. Any protocol-specified treatment requirement will be discontinued immediately at any time during the study at the request of the subject.
2. Investigator will discontinue any protocol-specified treatment requirement if the subject's health, safety, and/or well-being is threatened.
3. Protocol-specified treatment requirements will be discontinued and replaced with appropriate therapy for any subject who experiences or requires any of the following:
 - An increase in dose of any concurrent SLE medications (including but not limited to corticosteroids, immunosuppressives, and/or immunomodulatory medications such as azathioprine, methotrexate, leflunomide, mycophenolate, and/or hydroxychloroquine) or addition of a new immunosuppressive medication (including cyclophosphamide or rituximab). *Note:* corticosteroids may be increased for a maximum of 2 days for reasons unrelated to SLE disease activity provided the last dose is taken more than 5 days prior to the day 56 assessments (section 5.3)
 - A grade 3 or higher NCI-CTCAE (version 4.0) adverse event that is considered to be related to study therapy during the course of the study. The exception to this will be hemoglobin levels where a grade 3 level of 8 may be acceptable. This will depend on the hemoglobin level at study entry and the investigator's assessment of relationship to study drug. A requirement for blood transfusion would be considered a stopping point.
 - Pregnancy
 - If a subject enrolls in a concurrent interventional trial.

In addition, subject non-compliance with treatment regimens or failure to keep appointments may disrupt protocol-specified treatment requirements and necessitate permanent discontinuation of treatment procedures at the discretion of the investigator.

Finally, protocol specified treatment requirements will be discontinued as a natural consequence in subjects who are withdrawn from the study per the study guidelines.

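### The adverse event frequency has no new-or-worse-than-pre-dose condition for laboratory values, so unchanged entry abnormalities can be counted as on-treatment events

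*Combined protocol and SAP*

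**What the plan says.** Under Section 8.2.2, a laboratory or clinical result that the investigator finds to be "clinically significant or NCI CTCAE Grade 1 and above, it must be recorded as an adverse event". The two conditions are alternatives, so the grade is enough by itself. Section 8.2.1 opens the collection period at the first dose. Section 8.2.3 has events recorded whatever their severity or relation to the drug.

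Section 5.4.2 makes safety a secondary endpoint, namely how often adverse events (serious ones among them) occur, with laboratory results counted: "including measurements of hematology, clinical chemistry, lipid profile and urinalysis parameters over the course of the study from baseline to day 56". It adds: "All adverse events will be mapped into their MedDRA preferred terms". Section 7.1.1 puts everyone who took at least one dose into the adverse event analyses and summarises categorical data by counts and percentages. Section 8.4 summarises safety data for the treatment period and for the whole study.

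The one stated exemption is in Section 8.1: "laboratory test abnormalities reported as part of a lupus flare will not be separately reported as an adverse event".

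Two other rules do look at the entry state. Flare grading in 8.1 requires a change: "Moderate lupus flare (Grade 2): New BILAG 2004 grade B in one or more organ systems". For hemoglobin, the discontinuation rule in 6.1 says "a grade 3 level of 8 may be acceptable. This will depend on the hemoglobin level at study entry".

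The exclusion criteria in Section 5.2 leave room for abnormal values at entry. Liver enzymes are excluded only at "ALT or AST ≥ 2 x upper limit of normal at screening", pancreatic enzymes only at "amylase/lipase >3 x upper limit of normal at screening", and hemoglobin only below 8 g/dL. No limit is set for white cells or platelets.

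**The concern.** A frequency of events on treatment is normally read as what happened after the drug was started. Here a subject who enters with a stable grade 1 or higher abnormality, from lupus or background medication, meets the recording rule again when blood is drawn on Day 14, 28, 56 or 84. Nothing in the planned tabulation separates that value from one that appeared after dosing.

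There is no control arm whose background rate could be subtracted. Safety and tolerability is the first secondary objective, and the frequency of adverse events is how it will be judged. The bias runs one way, towards making nelfinavir look less well tolerated. It matters most in tables by laboratory term, where genuine new events may be few.

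**Working it through.** **Step 1: is there a baseline condition anywhere in the text?** No figure in the plan bears on this, so the first check is a comparison of the relevant sections.

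| Section | Subject | New or worse than pre-dose required? |
|---|---|---|
| 5.4.2 | Safety endpoint | No; its baseline-to-Day-56 wording reads as a time window |
| 7.1.1 | Safety set and summaries | No |
| 8.1 | Adverse event definition | No explicit condition |
| 8.1 | Lupus flare grades | Yes |
| 8.2.1 | Collection period | No; sets the start only |
| 8.2.2 | Recording of abnormal values | No; its mention of baseline governs how long a test is repeated |
| 8.2.3, 8.3.1 | Recording, grading | No |
| 8.4 | Safety summaries | No |
| 6.1 | Hemoglobin and discontinuation | Entry level considered, for discontinuation only |

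**Step 2: can a permitted entry value meet the rule?** Yes, for at least one test. Hemoglobin of exactly 8 g/dL is not excluded by 5.2, and 6.1 labels that level grade 3. For liver and pancreatic enzymes, white cells and platelets, the answer depends on the CTCAE cut-offs, which the protocol does not reproduce.

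**Step 3: effect on the share of subjects with any adverse event.** Let t be the share with a truly new or worsened event and p the share entering with a stable value of grade 1 or above. Both are assumed, and taken as independent. The recorded share is 1 − (1 − t)(1 − p), so the excess is p(1 − t). In percentage points:

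| t | p = 10% | p = 25% | p = 50% |
|---|---|---|---|
| 20% | 8 | 20 | 40 |
| 40% | 6 | 15 | 30 |
| 60% | 4 | 10 | 20 |
| 80% | 2 | 5 | 10 |

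For example, with t = 40% and p = 25% the recorded share is 1 − 0.60 × 0.75 = 55% instead of 40%.

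**Step 4: effect on a single laboratory term.** With an assumed 5% truly new, the recorded share is 1 − (1 − p)(0.95):
- p = 5%: 1 − 0.95 × 0.95 = 9.75%
- p = 10%: 1 − 0.90 × 0.95 = 14.5%
- p = 20%: 1 − 0.80 × 0.95 = 24%

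**Step 5: stopping limits in 5.4.2.** Suppose a share q of subjects each contributes one unchanged grade 3–4 value, all of the same type (the least favourable case for the same-type limits). The exact binomial probability that these values alone reach each limit is:

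| Limit | q = 5% | q = 10% |
|---|---|---|
| 3 of first 4 (same type) | 0.05% | 0.37% |
| 4 of first 4 (any type) | 0.00% | 0.01% |
| 4 of first 13 (same type) | 0.31% | 3.42% |
| 5 of first 13 (any type) | 0.03% | 0.65% |
| 10 of 43 (same type) | 0.00% | 0.87% |
| 15 of 43 (any type) | 0.00% | 0.00% |

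**The case against.** The best reply is that 8.2.2 should not be read alone. Section 8.1 defines an adverse event as an untoward occurrence associated with use of a drug. Section 8.2.2 introduces abnormal values only as possible signs of an event, and repeating a test until it goes back to baseline presupposes that it had left baseline. Medical history is taken before dosing, so existing conditions have a place to go. A sensible site might therefore leave unchanged values out. That is a fair guess at intent, but it is an inference set against an explicit instruction to record, and nothing in the analysis text restores the condition.

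The Data Safety Monitoring Plan and the manual of procedures, to which Section 8 refers, may contain a baseline rule. They are not among the documents reviewed, so the point is confined to the protocol text.

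Attribution (8.3.2) helps only in part. It is a judgement on each event by the site investigator, and the endpoint counts events regardless of it. Most pre-dose laboratory values are collected, so change from entry could be derived later, but no such derivation is planned.

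One part of the opposing case stands fully: broad recording is a defensible, cautious choice in a single-arm study. A reader might infer that 8.2.2 itself should be narrowed. That would do harm. The stopping limits in 5.4.2 and expedited reporting in 8.4.1 both operate on adverse events, so narrowing the recording rule could remove unchanged grade 3–4 values from both.

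**Conclusion.** The point holds as a modest weakness in how the safety endpoint is tabulated. On the literal text, unchanged entry abnormalities, at least hemoglobin near 8 g/dL, count towards the adverse event frequency and bias it upward. The shares p, t and q above are assumptions. If most subjects have some genuine grade 1 event, which is plausible, the overall share moves little and the distortion sits mainly in individual laboratory terms.

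Three stronger readings are not supported. First, a reader might infer a large known inflation; the documents give no entry prevalence, and only for hemoglobin do they show that a permitted value is graded. Second, a reader might infer that the efficacy conclusion is at risk; the primary decision rests on percent change in anti-dsDNA titer, and adverse event counts do not enter it. Third, a reader might infer that the stopping limits will be triggered spuriously; from unchanged values alone, each limit is reached with probability of at most 3.4% even at q = 10%, so this is negligible unless many subjects enter at grade 3–4.

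This is a cheap improvement to a descriptive secondary endpoint.

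**What to change.** Leave recording in 8.2.2, the stopping limits in 5.4.2 and expedited reporting in 8.4.1 unchanged. Add to 5.4.2 and 7.1.1:

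*Adverse events based on laboratory values are tabulated as treatment-emergent if the CTCAE grade is new or at least one grade higher than in the last available pre-dose value of that test (screening or Day 1, whichever is later), or if the investigator judged the value a clinically significant change from before dosing. All recorded events are also listed. Values with no pre-dose result are counted as treatment-emergent.*

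State that the treatment-emergent frequency is the reported safety endpoint.

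Using the last available value matters for lipids, which are measured before dosing only at screening, not on Day 1. Amylase and lipase are absent both from the screening laboratory list and from the Day 1 list for subjects returning within 10 days. Those subjects may therefore have no pre-dose result, although exclusion 8 refers to one. Counting their abnormal values as treatment-emergent is conservative.

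The cost is a few sentences and a little more analysis work. No new sample or visit is required.

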8.2.3 Recording Adverse Events

Throughout the study, the investigator will record and grade adverse events on the appropriate AE case report form (AE CRF) regardless of their severity or relation to study medication or study procedure. All requested information on the AE CRF should be provided, if available.

8.2.4 Recording Serious Adverse Events

Serious AEs will be recorded on the appropriate SAE CRF. All requested information on the SAE CRF should be provided, if available.

8.3 Grading and Attribution of Adverse Events

8.3.1 Grading Criteria

The study site will grade the severity of adverse events experienced by the study subjects according to the criteria set forth in the National Cancer Institute's Common Terminology Criteria for Adverse Events Version (NCI CTCAE) 4.0. This document (referred to herein as the NCI-CTCAE manual) provides a common language to describe levels of severity, to analyze and interpret data, and to articulate the clinical significance of all adverse events. Note: all adverse events are to be reported and graded, whether or not related to disease progression or intervention.

Adverse events will be graded on a scale from 1 to 5 according to the following standards in the NCI-CTCAE manual:

Grade 1 = mild adverse event.

Grade 2 = moderate adverse event.

Grade 3 = severe and undesirable adverse event.
Grade 4 = life-threatening or disabling adverse event.
Grade 5 = death.

8.3.2 Attribution Definitions

The relation, or attribution, of an adverse event to an investigational product will be determined by the site investigator. The site investigator will also record the determination of attribution on the appropriate CRF and SAE reporting form. The relation of an adverse event to the study intervention will be determined using the following descriptors and definitions:

- Unrelated: The adverse event is clearly not related to the investigational agent(s).
- Unlikely: The adverse event is doubtfully related to the investigational agent(s).
- Possible: The adverse event may be related to the investigational agent(s).
- Probable: The adverse event is likely related to the investigational agent(s).
- Definite: The adverse event is clearly related to the investigational agent(s).

8.4 Reporting of Adverse events

All patients who receive at least one dose or part of a dose of the trial medication and complete a safety follow-up, whether withdrawn prematurely or not, will be included in the safety analyses. All data relating to safety will be listed and summarized separately for the treatment period and for the entire study.

All safety reports will be reviewed by the Sponsor Site PI, [name], and the Steering Committee in addition to the Safety Officer appointed by NIAMS.

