6.1.1 Procedures for Discontinuation of Protocol –Specified Treatment Requirements and Follow-Up

For subjects who have been discontinued from protocol-specified treatment requirements but have not withdrawn consent, the following procedures will apply:

1. The subject will be asked to complete a discontinuation visit at the time of study discontinuation that will include a physical exam, lupus disease assessments as applicable (SLEDAI, BILAG, joint count), SLICC, LupusPRO, PGA, cbc, chemistry, C3, C4, anti-dsDNA and mechanistic studies.
2. If discontinuation is due to safety concerns, the subject will be given appropriate care under medical supervision, until the symptoms of any adverse event resolve or the subject's condition becomes stable.

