6.2 Subject Withdrawal from the Study

When a subject is withdrawn from the study, protocol-specified treatment requirements are discontinued, and study-related visits, exams, procedures, assessments, tests and data collection are terminated. Individual subjects will be withdrawn from the protocol under the following conditions:

1. The subject withdraws consent.
2. The investigator believes it is in the best interest of the subject.
3. Subjects who are lost to follow-up will also be regarded as withdrawn from the protocol.

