7.1.1 Handling of Dropouts and Non-Evaluable Subjects

For the evaluation of efficacy using the Simon Two-Stage Optimal Design rule, any subject who is not evaluable or drops out from the study for any reason (including adverse events), will be replaced by a new subject. The subject being replaced will not be used in the analysis of efficacy. As noted elsewhere in this protocol, a subject will be considered “evaluable” for efficacy if he/she has complied with at least 80% of the prescribed medication dosing over the entire 56 days of medication administration ($<80\%$ is “not evaluable”). This “per protocol” rule has been implemented since this is a Phase II efficacy trial and the “intention-to-treat” principle does not apply. In order to account for a standard dropout rate of 20%, the potential maximum number of subjects to be enrolled will increase to 51 subjects.

For the evaluation of safety, any subject who is exposed to at least one dose of the medication will be included in all analyses of adverse events, even if this subject is replaced under the efficacy rule cited above.

The statistical analysis for the primary endpoint, therefore, is a straightforward calculation of percent change within each subject in anti-dsDNA antibody titer from baseline to 8 weeks. We have defined a clinically meaningful decrease in anti-dsDNA antibody titer to be a decrease in titer that is $\geq 35\%$; this is based on serologic data from a previous study comparing the efficacy of prednisone compared to placebo for disease flare prevention in serologically active, clinically stable SLE subjects [39]. For other secondary endpoints, descriptive statistics on continuous

measurements will include means, medians, standard deviations, and ranges, while categorical data will be summarized using frequency counts and percentages.

8. SAFETY MONITORING AND REPORTING (please also reference the Data Safety Monitoring Plan and sections 3.n-3.o of the MOOP)

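### Sections 7.1.1 and 8.4 define the safety population differently; read literally, 8.4 leaves out dosed subjects who die, are lost or withdraw before completing an undefined safety follow-up

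*Combined protocol and SAP*

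**What the plan says.** Two sections state who enters the safety analyses.

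- Section 7.1.1, in the statistical chapter: "any subject who is exposed to at least one dose of the medication will be included in all analyses of adverse events". The sentence goes on to keep replaced subjects: "even if this subject is replaced under the efficacy rule cited above".
- Section 8.4, in the safety chapter: "All patients who receive at least one dose or part of a dose of the trial medication and complete a safety follow-up", continuing "whether withdrawn prematurely or not, will be included in the safety analyses".

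Three other sections bear on whether a subject can complete a follow-up.

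- Section 8.2.1 collects adverse events from the first dose "until he/she completes study participation on Day 84 or until 30 days after he/she prematurely withdraws from the study".
- Section 6.2 says that on withdrawal "study-related visits, exams, procedures, assessments, tests and data collection are terminated", and adds: "Subjects who are lost to follow-up will also be regarded as withdrawn from the protocol".
- Section 6.1.1 covers subjects who stop treatment but keep their consent: "The subject will be asked to complete a discontinuation visit at the time of study discontinuation".

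**The concern.** Both rules govern the same tables but need not select the same subjects. The rule in 7.1.1 depends only on exposure. The rule in 8.4 also depends on something that happens after dosing, and so may depend on how the subject fared on the drug. A subject who dies or disappears may have adverse events on record and still be left out because a later follow-up was not completed.

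Safety and tolerability is the first secondary objective listed, Section 5.4.2 evaluates safety by the frequency of adverse events, and there is no placebo arm. No comparison group would share and offset a distortion in numerator or denominator. In an open-label trial, two competing definitions also let the analyst settle the denominator once the events are known.

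**Working it through.** The plan states no figure on this point, so the check is a comparison of texts followed by a short expression for the possible bias.

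**1. What 8.4 adds.** It joins dosing and completed follow-up with *and*. The clause on premature withdrawal says that withdrawal does not by itself exclude a subject; it does not lift the follow-up condition. A withdrawn subject who completes the follow-up is in, and one who does not is out.

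**2. What the follow-up could be.** The documents do not define it. Candidates are the Day 84 visit, the end of the 30-day period in 8.2.1, the discontinuation visit in 6.1.1, or any safety contact after dosing. The table takes a strict reading (Day 84 or the 30-day period completed) and a lenient one (any contact after dosing).

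| Dosed subject | 7.1.1 | 8.4, strict | 8.4, lenient |
|---|---|---|---|
| Completes Day 84 | in | in | in |
| Withdraws early, 30-day collection completed | in | in | in |
| Withdraws, data collection ends at once under 6.2 | in | out | in, if seen once after dosing |
| Dies on treatment after at least one visit | in | out | in |
| Lost after at least one post-dose visit | in | out | in |
| Never seen after the first dose | in | out | out |
| Took only part of a dose, follow-up completed | unclear | in | in |

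The last row is a second, smaller difference: the part-dose wording stands in 8.4 and not in 7.1.1. On a literal reading, neither set wholly contains the other.

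**3. Whether a withdrawn subject can complete a follow-up.** Section 6.2 ends data collection at withdrawal and counts lost subjects as withdrawn. Section 8.2.1 continues adverse event collection for 30 days. The two give different answers.

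**4. Direction of the bias.** Let *N* be the number dosed, *m* the number without completed follow-up, *p*₁ the proportion with an event among those with follow-up, and *p*₀ the proportion among those without.

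- Frequency under 7.1.1: [(*N* − *m*)*p*₁ + *m* *p*₀] / *N*
- Frequency under 8.4: *p*₁
- 7.1.1 minus 8.4: (*m*/*N*)(*p*₀ − *p*₁)

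The 8.4 figure is too low if *p*₀ > *p*₁, equal if *p*₀ = *p*₁, and too high if *p*₀ < *p*₁. The documents give none of *m*, *p*₀ or *p*₁.

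**5. Scale of a single case.** Assume that all 51 subjects of the maximum enrolment in 7.1.1 are dosed, one dies on treatment, and the other 51 − 1 = 50 complete follow-up. Under 7.1.1 the death appears as 1/51 = 2.0%. Under the strict reading of 8.4 it appears as 0/50. This shows what one exclusion does; it is not an estimate.

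**6. What carries no follow-up condition.** The stopping rules in 5.4.2, expedited reporting in 8.4.1 and the six-monthly listing of adverse events in 8.4.2 do not depend on completed follow-up. Only the summary safety analyses are exposed.

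**The case against.** Much can be said for the plan.

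- **Withdrawn subjects are addressed.** A reader might infer that everyone who withdraws drops out under 8.4. The text does not support that, since it expressly keeps prematurely withdrawn subjects who have the follow-up. This stands, and the point is limited accordingly.
- **The term may be meant loosely.** The wording asks for *a* follow-up, which could be any safety contact after dosing. Visits fall on Days 7, 14 and 28, so only subjects never seen after dosing would then be lost. The Data Safety Monitoring Plan and Manual of Procedures, to which Section 8 refers, are not among the documents and might define it. This is a fair reading, but the protocol does not state it, and even so 8.4 remains narrower than 7.1.1 for subjects never seen again.
- **Those who stop for toxicity are followed.** Under 6.1.1 they are asked to a discontinuation visit and, for safety stops, receive care until events resolve or the condition is stable; 8.2.2 follows recorded events in the same way. A reader might infer that 8.4 systematically removes subjects who stop for toxicity. The documents do not support that: unless they withdraw consent, these subjects may be among the best followed. What stands is that deaths, losses and withdrawals before completion can be related to toxicity, so downward bias is possible but not established.
- **Oversight does not depend on 8.4.** This stands. A death would still be reported promptly and would appear in the six-monthly listing.
- **The statistical chapter already has the inclusive rule.** That is so, but nothing gives it precedence over 8.4.

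**Conclusion.** The two definitions conflict and the documents do not resolve the conflict. Read literally, 8.4 leaves out dosed subjects who die, are lost, or withdraw before completing the undefined follow-up, although their adverse events may have been recorded. The summary frequencies would be biased downward if missing follow-up is related to toxicity, and unbiased, with a smaller denominator, if it is unrelated. In either case the denominator is left open.

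The number affected cannot be derived. A reader might take it from the enrolment figures, 51 − 43 = 8 subjects, or 8/51 = 15.7%. The documents do not support this. Those 8 are places for efficacy replacements, which include subjects below 80% compliance who may attend every visit. Nor is 8 a ceiling, because an evaluable subject can miss follow-up after Day 56.

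The primary endpoint, the two-stage decision rule, the stopping rules and ongoing safety reporting are not affected. The fault lies in the descriptive safety summaries of an exploratory trial. It should still be corrected before analysis, since those summaries are the trial's main safety result and the correction costs almost nothing.

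**What to change.** 1. In 8.4, delete the condition that a safety follow-up be completed.
2. Use one definition in both 7.1.1 and 8.4 for all safety summaries: every subject who receives at least one dose or part of a dose, with no follow-up condition. This also means adding the part-dose wording to 7.1.1, where it is now absent.
3. Report the number of subjects without completed follow-up as a footnote to the safety tables, not as an exclusion, and state there what counts as completed.
4. Reconcile 6.2, which ends data collection at withdrawal, with 8.2.1, which collects adverse events for 30 days after premature withdrawal, so that it is clear what data exist for withdrawn subjects.

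The cost is an edit to a few sentences, with no extra subjects or visits needed to change the analysis population. The reported event frequency may become slightly less favourable.
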